#### 8.8.3. Notifying the Safety Review Committee

The Emmes Coordinating Center will provide the SRC with listings of all SAEs on an ongoing basis. Furthermore, the SRC will be informed of expedited reports of SAEs.

#### 8.8.4. Notifying the Institutional Review Board

The PI will ensure the timely dissemination of required AE information, including expedited reports, to the IRB in accordance with applicable local regulations and guidelines. The PI is responsible for submitting the IND Safety Report (initial and follow up SAE reports) or other safety information (e.g., revised IB) to the site's IRB and for retaining a copy in the site's study file.

#### 9. SAFETY MONITORING

Extensive safety monitoring will be provided for this protocol. The PI and/or designated site staff will be responsible for continuous close safety monitoring of all study participants and for alerting the Sponsor if unexpected concerns arise or pause criteria are met.

#### 9.1. Safety Review Committee

A Safety Review Committee, comprised of the PI, a medical expert with experience in vaccine pharmacovigilance not involved with the study, the Emmes medical monitor, SIIPL and PATH medical officer will monitor safety throughout the duration of the study. The Emmes study statistician with assistance of the data management staff will prepare safety reports as needed for SRC discussions. During the vaccination period the SRC will review weekly the safety data. At any time during the study, the Emmes Coordinating Center will notify the SRC of ad hoc review if pause criteria may have been met. The SRC reviews will be summarized with consensus recommendations to the study Sponsor as to whether there are safety concerns and whether the study should continue without change, be modified, or be stopped. The SRC may request review of unblinded safety data by the pharmacovigilance expert in its deliberation. SRC consensus recommendations regarding modifying or stopping further enrolment may involve Sponsor consultation with the local regulatory authority.

The SRC members must be satisfied that the timelines, completeness, and accuracy of the data submitted to them for review are sufficient. Items reviewed by the SRC may include: study participant demographic information; interim/cumulative data for evidence of study-related AEs; data quality, completeness, and timeliness; and factors external to the study, such as scientific or therapeutic developments that may impact participant safety or the ethics of the study. If at any time, a decision is made to discontinue administration of study product in all participants, expeditious notification will be provided by the sponsor to the US FDA and by the PI to the site IRB.

## 9.2. Study Pause Rule

The following study pause rules will automatically pause or halt further vaccinations. However participants already enrolled will continued to be followed for safety during the pause. These pause rules refer to suspected adverse reactions and will be triggered automatically if any of the event described below are met during the conduct of the study:

- One or more participants experience a serious adverse reaction.
- One or more participants experience a Grade 4 injection site reaction.
- Two or more participants experience the same Grade 3 injection site reaction.
- Two or more participants with the same severe (Grade 3) systemic reactogenicity signs or symptoms, within seven days following vaccination.
- Two or more participants experience the same vaccine-related Grade 3 or higher clinical (including fever) or laboratory abnormality.

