#### **SAFETY MONITORING:**

A Safety Review Committee (SRC) comprised of the Principal Investigator (PI), a medical expert with experience in vaccine pharmacovigilance not involved with the study, the Emmes medical monitor, Sponsor medical officer and SIIPL medical expert will be established to monitor participant safety throughout the duration of the study. The Emmes study statistician, with assistance of the data management staff, will prepare safety reports as needed for SRC discussions.

During the vaccination period, the SRC will review weekly the safety data. At any time during the study, the Emmes Coordinating Center will notify the SRC of ad hoc review if pause criteria may have been met.

The SRC reviews will be summarized with consensus recommendations to the study Sponsor as to whether there are safety concerns and whether the study should continue without change, be modified, paused or stopped. The SRC may request review of unblinded safety data by the vaccine pharmacovigilance expert in its deliberation. SRC consensus recommendations regarding modifying or stopping further enrolment may involve Sponsor consultation with the local regulatory authorities.

If at any time, a decision is made to discontinue administration of study product to all volunteers, expeditious notification will be provided by the sponsor to the US Food and Drug Administration (FDA), and by the PI to the University of Maryland, Baltimore (UMB) Institutional Review Board (IRB).

The following study pause rules will automatically pause or halt further vaccinations. However, volunteers already enrolled will continued to be followed for safety during the pause. These pause rules refer to suspected adverse reactions and will be triggered automatically if any of the event described below are met during the conduct of the study:

- One or more participants experience a serious adverse reaction.
- One or more participants experience a grade four injection site reaction.
- Two or more participants experience the same grade three injection site reaction.
- Two or more participants with the same severe (grade three) systemic reactogenicity signs or symptoms, within seven days following injection.
- Two or more participants experience the same vaccine-related grade three or higher clinical (including fever) or laboratory abnormality.

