#### 8.7. Adverse Event Identification, Resolution and Reporting

To improve the quality and precision of acquired AE data, the PI should observe the following guidelines:

- Whenever possible, use recognized medical terms when recording AEs on the AE CRF. Do not use colloquialisms and/or abbreviations.
- If known, record the diagnosis (i.e., disease or syndrome) rather than component signs, symptoms and laboratory values on the AE CRF (e.g., record congestive heart failure rather than dyspnea, rales, and cyanosis). However, signs and symptoms that are considered unrelated to an encountered syndrome or disease should be recorded as individual AEs on the CRF (e.g., if congestive heart failure and severe headache are observed at the same time, each event should be recorded as an individual AE).

Page **55** of **106** 

AEs occurring secondary to other events (e.g., sequelae) should be identified by the
primary cause. A "primary" AE, if clearly identifiable, generally represents the most
accurate clinical term to record on the AE CRF. If a primary serious AE (SAE) is recorded
on an SAE CRF, events occurring secondary to the primary event should be described in
the narrative description of the case.

For example:

Orthostatic  $\rightarrow$  Fainting and  $\rightarrow$  Head  $\rightarrow$  Neck pain hypotension fall to floor trauma

The primary AE is orthostatic hypotension.

- Grade 2 or higher abnormal laboratory test results will be reported as AEs and assessed
  for severity according to severity grading criteria provided in Appendix II and causality
  (related or unrelated) to the study product. Grade 1 abnormal laboratory test results will
  be entered as AEs if the site PI determines them to be clinically significant.
- Death is an outcome of an event. The event that resulted in the death should be recorded and reported on the SAE CRF.
- For hospitalizations for surgical or diagnostic procedures, the illness leading to the surgical
  or diagnostic procedure should be recorded as the SAE, not the procedure itself. The
  procedure should be captured in the case narrative as part of the action taken in response
  to the illness.
- Pregnancies that occur in study participants are not considered AEs and will be recorded on a separate Pregnancy CRF. Pregnancy outcomes that include stillbirth and any congenital anomalies must be reported as SAEs.

AEs may be discovered through any of these methods.

- Observing the participant.

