#### 6.6.2 Study Pause Rule

The following study pause rules will automatically pause or halt further vaccinations. However participants already enrolled will continue to be followed for safety during the pause. These pause rules refer to suspected adverse reactions and will be triggered automatically if any of the events described below are met during the conduct of the study:

- One or more participants experience a serious adverse reaction.
- One or more participants experience a Grade 4 injection site reaction.
- Two or more participants experience the same Grade 3 injection site reaction.
- Two or more participants experience the same severe (Grade 3) systemic reactogenicity signs or symptoms, within seven days following vaccination.
- Two or more participants experience the same vaccine-related Grade 3 or higher clinical (including fever) or laboratory abnormality.

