### 14.3.3 Narratives of Deaths, Other Serious and Significant Adverse Events

[This is a place holder for this section in the CSR.]

TABLE 14.3.4.1: Laboratory Results by Parameter, Maximum Severity, Study Day, and Treatment Group - Full Analysis Population

		None	Mild / Grade 1	Moderate / Grade 2	Severe / Grade 3	Life-Threatening / Grade 4	Missing
Treatment Group	N	n (%)	n (%)	n (%)	n (%)	n (%)	n (%)
Baseline							
Adjuvanted MCV-5	Х	x (xx.x)	x (xx.x)	x (xx.x)	x (xx.x)	x (xx.x)	x (xx.x)
Non-Adjuvanted MCV-5	Х						
Menactra ®	X						
Day 8						 	
Adjuvanted MCV-5	X						
Non-Adjuvanted MCV-5	х						
Menactra ®	х						
Maximum Severity Post-I	Baselin	ne 				 	
Adjuvanted MCV-5	X						
Non-Adjuvanted MCV-5	х						
Menactra ®	х						

<sup>1 Includes values collected at unscheduled visits.

Table 14.3.4.1: Laboratory Results by Parameter, Maximum Severity, Study Day and Treatment Group - Full Analysis Population (Continued)

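### One related, non-serious Grade 4 systemic, clinical or laboratory event triggers no automatic pause, although one Grade 4 injection site reaction does

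*Protocol*

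**What the plan says.** Protocol 9.2 gives five rules that halt vaccination automatically. They are bulleted there and are numbered 1 to 5 here in the order listed. The lead-in limits them all: "These pause rules refer to suspected adverse reactions". Protocol 8.5 equates a suspected reaction with a related event.

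- Rule 1: one participant with a serious adverse reaction.
- Rule 2: "One or more participants experience a Grade 4 injection site reaction".
- Rule 3: two participants with the same Grade 3 injection site reaction.
- Rule 4: "Two or more participants with the same severe (Grade 3) systemic reactogenicity signs or symptoms, within seven days following vaccination".
- Rule 5: "Two or more participants experience the same vaccine-related Grade 3 or higher clinical (including fever) or laboratory abnormality".

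The synopsis (Safety Monitoring) has the same list, including "One or more participants experience a grade four injection site reaction". So does SAP 6.6.2, whose rule 4 reads "Two or more participants experience the same severe (Grade 3) systemic reactogenicity signs or symptoms, within seven days following vaccination".

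Protocol 9.2.1 adds a discretionary route. If the principal investigator (PI) or designee, the medical monitor or any Safety Review Committee (SRC) member proposes a pause, vaccination and enrollment are suspended and the SRC convenes within 48 hours.

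**The concern.** Rule 2 treats one Grade 4 event as enough to stop, whether or not it is serious, but only at the injection site. A related Grade 4 systemic, clinical or laboratory event in one participant stops vaccination only if it is also judged serious. Otherwise the automatic rules wait for a second participant with the same event. The documents give no reason for the difference.

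This is a first-in-human study (Protocol 1.6), and the pause rules are meant to work without anyone having to decide. At stake is whether vaccination continues by default after a first Grade 4 laboratory value or fever attributed to the vaccine.

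**Working it through.** **The plan's own figures.** Protocol 7.4 describes 20 recipients per group. The chance of seeing an event with an 11% rate is 1 − 0.89^20 = 0.903. The one-sided 95% upper bound after no events is 1 − 0.05^(1/20) = 0.139. Both agree with the protocol (more than 90%, about 14%). Neither concerns the pause rules, for which the documents state no operating characteristics.

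**Rule check.** Take one participant with a related, non-serious Grade 4 laboratory value.

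- Rule 1 is not met: the event is not serious.
- Rules 2 and 3 are not met: it is not at the injection site.
- Rules 4 and 5 are not met: each needs a second participant with the same event.

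A Grade 4 systemic symptom that is not serious gives the same result.

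**Can a Grade 4 event be non-serious?** Protocol 8.4 labels Grade 4 life threatening. The life-threatening criterion in 8.3.2, however, requires immediate risk of death in the opinion of the PI or sponsor, so grade and seriousness are separate judgements. For laboratory values, Protocol 8.7 says "Grade 2 or higher abnormal laboratory test results will be reported as AEs and assessed" for severity and causality, which does not make them serious adverse events. SAP Table 14.3.4.1 has a column headed "Life-Threatening / Grade 4". Rule 2 points the same way: if every Grade 4 reaction were serious, rule 1 would already cover it.

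**Size.** Inputs:

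- n = 60 participants (synopsis).
- q = rate of one type of related, non-serious Grade 4 event. Assumed.
- r = rate of related Grade 3 events of the same type, which rule 5 also counts. Assumed.
- At most one such event per participant, equal rates in all participants, discretionary pauses ignored.

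The present rule pauses when two or more participants have the event at Grade 3 or higher:

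P(present) = 1 − (1−q−r)^n − n(q+r)(1−q−r)^(n−1)

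The amended rule also pauses on a single Grade 4 event:

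P(amended) = 1 − (1−q−r)^n − n·r·(1−q−r)^(n−1)

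The gain is n·q·(1−q−r)^(n−1), the chance that exactly one participant has the event and has it at Grade 4.

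Example with q = r = 0.5%: 0.99^60 = 0.5472 and 0.99^59 = 0.5527. Present: 1 − 0.5472 − 60 × 0.010 × 0.5527 = 0.121. Amended: 1 − 0.5472 − 60 × 0.005 × 0.5527 = 0.287.

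| q (Grade 4) | r (Grade 3) | Amended | Present | Gain, points |
|---|---|---|---|---|
| 0.1% | 0 | 5.8% | 0.2% | 6 |
| 0.5% | 0 | 26.0% | 3.7% | 22 |
| 0.5% | 0.5% | 28.7% | 12.1% | 17 |
| 0.5% | 2% | 51.2% | 44.4% | 7 |
| 1% | 0 | 45.3% | 12.1% | 33 |
| 1% | 2% | 64.0% | 54.1% | 10 |

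The gain shrinks as Grade 3 events of the same type become more common, because rule 5 then fires anyway. One factor works the other way: rule 5 needs the same event. If a total Grade 4 rate of 1% is spread evenly over four types with no Grade 3 events, the present rule pauses with probability 4.0% instead of 12.1%, and the amended figure stays at 45.3%. The formula sums, over m events, Binom(m; 60, 0.01) × [1 − 4·3·…·(4−m+1)/4^m].

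**The case against.** **Most Grade 4 events are already covered.** A life-threatening event, a hospitalization or an important medical event is serious under Protocol 8.3.2, and one related case meets rule 1. This largely stands. What remains is a related Grade 4 event judged not serious, in practice one graded by a numeric threshold. The Appendix II grading table is not in the text available for this review, so the cut-offs and the share of such events cannot be checked. Participants enter with acceptable laboratory values (4.3.1), and only one safety draw is scheduled after vaccination, at Day 8 (Appendix I).

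**The discretionary pause is strong.** It needs one person's proposal and no prior vote. This also stands, but it depends on someone choosing to act, whereas the rules in 9.2 are meant to be automatic.

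**It is a design choice.** Waiting for a second case before halting automatically on a non-serious event is defensible. It is harder to defend beside rule 2, which does not wait.

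**Stronger readings that the documents do not support.**

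- A reader might infer that the SRC could remain unaware for about 10 days: three days for data entry (10.1) plus seven to the weekly review (8.8.1, 9.1). But the PI or designee reviews laboratory results promptly (6.2), the PI sits on the SRC (9.1), and the PI can suspend vaccination by proposing a pause (9.2.1). The documents also give no accrual period from which to count further vaccinations.
- A reader might take 26.0% against 3.7% as the size of the gap. That pair holds only if Grade 3 events of the same type never occur.
- A reader might infer that rule 4, which names Grade 3 without higher grades, lets Grade 4 pairs escape. Rule 5 catches two related cases whether both are Grade 4 or one is Grade 3 and the other Grade 4.

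**Conclusion.** The gap is real but narrow. One related, non-serious Grade 4 systemic, clinical or laboratory event meets none of the five automatic rules, while one Grade 4 injection site reaction does. Rule 1 and the discretionary pause remove much of the practical risk but do not close the gap.

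At an assumed Grade 4 rate of 0.5%, a one-participant rule raises the chance of an automatic pause in 60 participants by about 22, 17 or 7 percentage points when the Grade 3 rate for the same event is 0, 0.5% or 2%. All these rates are assumptions, the figures ignore discretionary pauses, and the true frequency is unknown. The case for change rests on consistency in a first-in-human stopping rule and on the low cost of the change, not on a demonstrated large effect.

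**What to change.** Extend rule 2 in Protocol 9.2, the synopsis and SAP 6.6.2 to read: "One or more participants experience a Grade 4 injection site reaction", or a suspected (related) Grade 4 systemic reaction or clinical or laboratory abnormality.

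Cost: a protocol amendment that needs ethics approval before use (Protocol 12), matching SAP text, and an occasional extra pause with SRC review within 48 hours. At an assumed rate of 0.1%, the chance of at least one such event in 60 participants, and so of a pause, is 1 − 0.999^60 = 5.8%. Sample size, visits and endpoints do not change.

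Two tidying edits could go in with the amendment, but neither affects pausing in practice. Rules 3 and 4 could say Grade 3 or higher; rule 2 already covers Grade 4 at the injection site, and rule 5 covers systemic pairs. SAP 9.4.2 and Listings 16.2.7.1.1 and 16.2.7.1.2 stop at severe, while Protocol 8.4 and SAP Tables 14.3.1.3 and 14.3.1.4 go up to life threatening; the scale could be aligned.

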#### 9.2.1. Pause Procedure

- The SRC will be notified by the Emmes Coordinating Center and convene ad hoc review if pause criteria may have been met.
- At scheduled study review, the SRC may also identify adverse events that could potentially qualify as pause criteria.
- If the PI (or designee), the Emmes medical monitor or any member of the SRC identifies that a pause criterion may have been met or propose the study be paused on a discretionary basis, all vaccinations and enrollment will be suspended. The SRC will be notified and will expeditiously (within 48 hours) convene to review all available, relevant information. The SRC may request review of unblinded safety data by the pharmacovigilance expert, The SRC reviews will be summarized with consensus recommendations to the study Sponsor as to whether there are safety concerns and whether the study should continue without change, be modified, or be stopped.
- If at any time, a decision is made to discontinue administration of study product in all
  participants, expeditious notification will be provided by the Sponsor to the US FDA and
  by the PI to the IRB within 48 hours.
- If the Sponsor re-starts the study after SRC review and recommendation, enrollment and vaccination may resume.

#### 10. DATA MANAGEMENT

The PI is responsible for ensuring the accuracy, completeness, and timeliness of the data reported. Data collection is the responsibility of the clinical trial staff at the study site under the supervision of the study PI. The Emmes Corporation is responsible for data management activities, including quality review, analysis, and reporting of the study data according to Standard Operations Procedure (SOP).

## 10.1. Case Report Form Development and Completion

Electronic Data Capture will be the method of data collection in this study. The electronic Case Report Forms (eCRFs) will be developed by the Emmes Corporation and approved by SIIPL and PATH. Clinical data (including AEs, concomitant medications, and reactogenicity data) and clinical laboratory data will be entered into the 21 CFR Part 11-compliant Internet Data Entry System (IDES) provided by The Emmes Corporation. The data system includes password protection and internal quality checks, such as automatic range checks, to identify data that appear inconsistent, incomplete, or inaccurate. Clinical data will be entered directly from the source documents.

Data for each participant will be recorded in the eCRF. It is the PI's responsibility to ensure the accuracy, completeness, legibility, and timeliness of the data reported in the participant's eCRF and any supporting documentation. All source documents should be completed in a neat, legible manner to ensure accurate interpretation of data. Source documentation supporting the eCRF data should indicate the participant's participation in the study and should document the dates and details of study procedures, AEs and the participant's status. The PI/institution will maintain all information in the eCRFs and all source documents that support the data collected from each participant.

The PI or designated representative should complete the eCRFs as soon as possible but within three days after information is collected. Completed eCRFs must be submitted for each screened participant who signs the study-specific ICF. The eCRFs will not be completed for participants who do not sign the study specific ICF. The PI will retain all essential documents.

## 10.2. Details of Data Management

A Data Management Handbook (DMH) will be written by The Emmes Corporation and contain all study-specific requirements.

#### 10.2.1. Coding

The PI is responsible for ensuring the accuracy, completeness, and timeliness of the data reported. Data collection is the responsibility of the clinical trial staff at the study site under the supervision of the study PI. The Emmes Corporation is responsible for data management activities, including quality review, analysis, and reporting of the study data according to SOPs.

#### 10.2.2. Data Validation

The Emmes Corporation will inspect the data entered into the database for completeness and consistency.

#### 10.2.3. Source Data Verification

For source data verification (SDV), the monitor (on behalf of the study Sponsor) must have direct access to source documents that support the data recorded, e.g., medical records, original laboratory records and ICFs. If source data are electronic, these data must be printed, signed and dated by the PI and stored in the participant's study file. Clinical laboratory data will remain in study participant records. Essential documents, including ICFs, must be filed and kept in the study files on an ongoing basis.

#### 10.2.4. Definition of Source Data

Source data are all information in original records or certified copies of original records of clinical findings, observations, or other activities in a clinical study. Source data are contained in source documents.

